### **Number of Patients**

We wish for permission to enroll 20 patients in this study, all at New York Presbyterian/Weill Cornell Medical Center.

### **Data Analysis**

Data from all patients enrolled in the study will be reported.

We will calculate and report the proportion of patients for each endpoint.

## **ADVERSE EVENTS AND ASSESSMENT OF RISKS**

#### **Risk assessment and prevention:**

- Risks related to antithrombotic therapy: intracranial or systemic hematoma.  
Antithrombotic therapy is important to prevent stent thrombosis. According to the literature and our experience in patients with carotid and intracranial stenting, the risks related to anticoagulation are minimal. The benefit of administering two

medications (aspirin and clopidogrel) for 1 month and then continuing with aspirin alone has been demonstrated in large studies in patients with cardiac, carotid and intracranial stents. We will ask all female patients of childbearing age to avoid becoming pregnant during the time-course of anticoagulation. We will also instruct all patients to avoid contact sports and trauma.

- Risks related to general anesthesia: nausea, vomiting, fever, dizziness, headache, drowsiness, hoarseness, and sore throat.

Experienced anesthesiologists will administer general anesthesia using standard techniques. Pre-procedure evaluation and standard protocol for patient preparation (i.e. empty stomach) will be used to minimize the risks.

- Risks related to femoral vein puncture: hematoma at puncture site, pain at puncture site, infection, and thrombophlebitis.

To minimize the risks of femoral vein puncture we will use standard angiographic techniques in a sterile environment. In patients with difficulty in accessing the femoral vein (obesity), ultrasound can be used to guide the puncture.

- Risks related to venous sinus stent placement: venous rupture, venous thrombosis or occlusion, intracranial hematoma, progressive visual loss, stroke, death.

Although venous sinus stenting is a new procedure, review of the literature shows that complications are rare. In only two cases, retrograde venous angiography demonstrated thrombosed stent in the immediate postoperative course, necessitating thrombolysis. In these two cases, it was not mentioned whether the procedure was performed under anticoagulation only or if antiplatelet therapy was also administered.

In addition to the cases reporting venous sinus stenting for IIH, there is an additional recent report of treatment of 10 dural arteriovenous fistulas of the transverse sigmoid sinus using similar techniques of self-expanding stent placement and balloon angioplasty (Levrier O et al. 2006). In this series, one patient experienced a brain parenchyma hematoma secondary to the occlusion of a superficial cortical draining vein. That patient was not pre-medicated with anticoagulation prior to the procedure and since then the authors started using clopidogrel for 3 days prior to the procedure without further complications. All subjects of this protocol will be pretreated with

antiplatelet agents before the procedure (aspirin and clopidogrel). Pretreatment with these medications before the stent placement is routinely performed for patients undergoing coronary, carotid and intracranial stents. In addition, the procedure will be done under systemic administration of heparin, also routinely used for endovascular procedures. Therefore, the risk of stent or cortical vein thrombosis will be minimal.

- Risks related to administration of iodinated contrast: contrast allergy, contrast induced nephropathy.

To minimize the risk of contrast allergy and nephropathy, a standard screening questionnaire for iodinated contrast will be reviewed before the procedure. Patients at risk for allergy (i.e. prior severe allergic reaction) or at risk for contrast nephropathy (i.e. history or evidence of renal function impairment) will be excluded from the study (see exclusion criteria).

- Risks related to MRI scan: minimal risks.

We will use standard equipment and protocols. We will screen all patients for contraindications to MRI using standard questionnaire and interview.

Risks related to gadolinium (MRI contrast): contrast allergy, nephrogenic systemic fibrosis

Patients with compromised renal function are excluded from the study (see exclusion criteria) and thus the risk of nephrogenic systemic fibrosis from the use of MRI contrast is minimal.

- Risks related to invasion of privacy: minimal risks.

All personal data and medical records will be kept confidential according to hospital regulations and legal requirements. No participant in this study will be identified personally in any reports or publications.

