#### Exclusion criteria

- Tinnitus contralateral to dominant narrowed side for patients with bilateral transverse sinus stenosis
- Arterial Pulsatile Tinnitus
- Dural Arteriovenous Fistula or other vascular malformation of the brain, head or neck
- Paragangliomas
- Non-pulsatile tinnitus
- Otologic disorders
- Disorders involving vestibular system and balance
- Visual Field Defects or Papilledema consistent with increased intracranial pressure
- Lateral venous sinus thrombosis
- Contra-indication to iodinated contrast
- Contra-indication to antiplatelet therapy
- Contra-indication to general anesthesia
- Pregnancy or plans for immediate pregnancy

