#### **Screening Process**

The study will be announced to physicians via mail, email, presentations and talks. The information about the study will be available to the public on the Internet. All patients with complaints of tinnitus and who have failed previous non-invasive treatments will undergo comprehensive evaluation by an ENT physician, which will include comprehensive medical history and full head and neck exam. Otologic evaluation will consist of binocular microscopy, tuning fork exam, pneumatic otoscopy, audiogram, tympanometry, and auscultation for audible bruit. If indicated, imaging studies will be obtained as part of the standard tinnitus evaluation. For patients with pulsatile tinnitus,

vascular imaging studies of the brain, MRA, MRV, CTA, CTV, will be ordered. Imaging protocols for tinnitus vary depending on the patient's history and exam. All patients with venous pulsatile tinnitus considered for the trial will have at least MRA and MRV studies done as part of the work-up of venous pulsatile tinnitus. Patients with contraindication to MRI scans will be evaluated with CTA and CTV instead. This imaging work-up is important for screening and selection of patient but is not experimental and is not part of the trial. It should be done however within 6 months from enrollment. In addition to the previously mentioned imaging studies, every patient will be evaluated with an MRI of the Head and Temporal Bone (Internal Auditory Canal protocol) in order to rule out the presence of other causes of venous pulsatile tinnitus. Patients with contraindication to MRI will be evaluated with CT of the Head and Temporal Bone. The patients who are diagnosed with venous pulsatile tinnitus and in whom presence of venous sinus stenosis is confirmed by imaging studies, will be informed about the trial and provided with the contact information for enrollment. As there is variability in the normal diameter of the transverse venous sinuses in terms of the entire length of the sinus (Ayanzen 2014), a pathologic stenosis will be defined as a >50% decrease in caliber in a focal area or segment of the sinus when compared to the normal diameter before and after.

All patients will be required to have a comprehensive work-up of tinnitus and ENT evaluation within 6 months of enrollment in the trial.

Eligible patients will meet with the investigators to discuss inclusion and exclusion criteria, procedural details, risks and alternatives and sign the IRB consent form.

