### **Venous sinus stenting procedure**

#### Pre-procedure anti-thrombotic regimen

Patients will receive daily aspirin 325mg and clopidogrel (Plavix®) 75 mg for 7 days prior to the intervention.

Direct Retrograde Cerebral Venography (DRCV) and Manometry

The first part of the procedure is to perform a venography and manometry study, using standard angiographic techniques under local anesthesia. Vascular access is obtained from the femoral vein with placement of a 6 French sheath. Then the right or left jugular vein (per MRV or CTV findings) is catheterized with a 6 French guide catheter. A microcatheter is advanced distal to the stenosis and venography is performed. If at least 50% venous sinus stenosis is confirmed, venous sinus manometry is performed proximally and distally to the stenosis with a microcatheter. It is important to perform this part of the procedure without general anesthesia because general anesthesia may cause artificially elevated venous sinus pressures. Sinus catheterization with the soft microcatheters used for DRCV is painless and generally well tolerated. If the venous pressure gradient across the stenosis is  $\geq 4$  mmHg, we will proceed with stenting.

Venous sinus stenting

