The procedure requires general anesthesia because stent navigation into the venous sinuses can be painful. Vascular access is obtained from the femoral vein and a 6 French sheath catheter is positioned in the jugular vein. Subsequently, a microcatheter is navigated using standard neurointerventional techniques into the superior sagittal sinus. A venogram will be performed with contrast injection via the microcatheter to confirm the location and degree of stenosis. After the venogram, the microcatheter will be exchanged for an intravascular ultrasound catheter, and intravascular ultrasound will be performed to confirm degree of stenosis. Following this step, the intravascular ultrasound catheter will be withdrawn and balloon angioplasty will be performed across the stenosis, followed by deployment of a self-expandable stent (Cordis Precise-Pro Stent). An embolic protection device is not required and will not be used because there is no risk of cerebral embolism. After the catheters are removed, hemostasis at the puncture site is achieved with manual compression. In patients with stenosis on the dominant transverse sinus, the stent is placed in the dominant side. In patients with co-dominant transverse sinuses and bilateral stenosis, the stent is placed across the stenosis on the side of worse tinnitus.

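### The risk section twice cites a renal exclusion that the list of exclusion criteria does not contain

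*Protocol*

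**What the plan says.** Under *Adverse Events and Assessment of Risks*, the subsection *Risk assessment and prevention* treats renal impairment in two places.

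- **Iodinated contrast.** Screening is by questionnaire: "To minimize the risk of contrast allergy and nephropathy, a standard screening questionnaire for iodinated contrast will be reviewed before the procedure". Besides patients at risk of allergy, those "at risk for contrast nephropathy (i.e. history or evidence of renal function impairment) will be excluded from the study (see exclusion criteria".
- **Gadolinium.** "Patients with compromised renal function are excluded from the study (see exclusion criteria". The same sentence then infers that the risk of nephrogenic systemic fibrosis is minimal.

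The list under *Exclusion criteria* has one related line: "Contra-indication to iodinated contrast". Under *Screening Process*, the criteria are what is taken up at the consent meeting: "Eligible patients will meet with the investigators to discuss inclusion and exclusion criteria". That section also says what follows from a contraindication to MRI: "Patients with contraindication to MRI scans will be evaluated with CTA and CTV instead". *Imaging studies* makes the same substitution for the 12-month venogram.

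**The concern.** The risk section does not merely express an intention. It reports that a criterion is on the list and sends the reader there. A reader who follows either pointer finds no renal criterion.

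Two things depend on it. First, the risk section rests part of its protection against contrast nephropathy, and its whole argument on nephrogenic systemic fibrosis, on the exclusion. Second, eligibility has consequences in this protocol: under *Criteria for Early Termination of Treatment*, a significant departure from the eligibility criteria is a protocol violation and the patient is removed. As written, two careful readers could disagree on whether an enrolled patient with renal impairment is such a violation.

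**Working it through.** The Protocol gives no figure to reproduce. The check compares the texts and then bounds the contrast exposure.

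**1. What each section contains**

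| Protocol section | Entries or statements | Naming renal function | Naming gadolinium |
|---|---|---|---|
| Inclusion criteria | 7 | 0 | 0 |
| Exclusion criteria | 13 | 0 | 0 |
| Risk section, renal exclusion with pointer to the list | 2 | 2 | 1 (the gadolinium paragraph) |

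The 13 exclusions cover contralateral tinnitus, arterial tinnitus, fistula or other malformation, paraganglioma, non-pulsatile tinnitus, otologic disorders, vestibular disorders, visual field defect or papilledema, lateral sinus thrombosis, pregnancy, and contraindications to iodinated contrast, antiplatelet therapy and general anesthesia. One of the 13, iodinated contrast, is related to the point. *Screening Process* names no renal test, and the case report form has no renal field.

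**2. Applying both texts to the same patient**

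| Patient | By the exclusion list alone | By the risk section |
|---|---|---|
| Prior severe reaction to iodinated contrast | Excluded | Excluded |
| Renal impairment that the screener judges a contraindication to iodinated contrast | Excluded | Excluded |
| Past or mild renal impairment that the screener does not judge a contraindication | Eligible | Excluded |

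The texts part in the third row. The risk section excludes on any past or present impairment, whereas the list requires a contraindication and does not say that impairment is one.

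**3. Whether another safeguard supplies the missing entry**

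- The questionnaire covers nephropathy as well as allergy, but it is a screening tool and not a listed criterion. The Protocol times it only as before the procedure.
- All patients are screened for contraindications to MRI, but the stated consequence is CT imaging, not exclusion.

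**4. Size of the exposure**

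- Patients: 20 (*Number of Patients*).
- In-trial MR venograms: 1 per patient at 12 months, so 1 × 20 = 20 at most. The Protocol does not say they are contrast-enhanced, so gadolinium doses range from 0 to 20.
- Procedural venography: 2 steps per stented patient. In the diagnostic part, "A microcatheter is advanced distal to the stenosis and venography is performed". In the stenting part, "A venogram will be performed with contrast injection via the microcatheter to confirm the location and degree of stenosis". So 2 × 20 = 40 steps at most.

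These are ceilings over all patients, not counts of renally impaired patients. The documents give no rate of renal impairment, so that count is left unestimated.

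**The case against.** The strongest reply is that the iodinated-contrast entry already is the renal exclusion. The sentence on nephropathy stands under iodinated contrast and points to the list, so that entry is its natural target. Allergy is handled in the same way: it is not named in the list either, and only the risk section explains it. Since exclusion is from the whole study, a patient turned away under that entry never reaches the 12-month MR venogram, and no separate gadolinium entry is needed. The risk section is itself operative protocol text, so the intended rule is not in doubt.

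Much of this stands. The first pointer does have a plausible target, and that target would protect the later scan too. The timing of the questionnaire is also weak evidence of a gap. Before the procedure does not mean after consent, and eligibility is in any case not settled at consent, because the pressure gradient, an inclusion criterion, is measured in the first part of the procedure.

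The gap remains for two reasons. The parallel with allergy is incomplete: a prior severe reaction to an agent is a contraindication to it in ordinary usage, whereas renal impairment of any degree, past or present, is not evidently one. And the gadolinium sentence is categorical, concerns another agent, and matches no entry in the list. The rule can be recovered only by reading a risk paragraph into a short line about a different contrast medium.

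**Conclusion.** The point holds: the Protocol is wrong as written. It twice reports a listed renal exclusion, and 0 of 13 exclusion entries state one. The list and the stated safety rule give different answers for patients whose renal impairment falls short of a judged contraindication to iodinated contrast.

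This should be corrected, but the practical exposure is small: 0 to 20 in-trial gadolinium doses and at most 40 procedural venography steps in 20 patients. No endpoint, sample size or planned calculation is affected. The conclusion assumes that the exclusion list is complete as shown, and it shows no gap or redaction. It also assumes that a screener may work from the list alone. A site that also applies the risk section would exclude these patients as intended.

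**What to change.** Add one entry to *Exclusion criteria* that excludes any past or current renal function impairment, using the parenthetical definition in the iodinated-contrast paragraph, and state that it applies to both iodinated contrast and gadolinium. Both pointers in the risk section then lead to a real entry, and the reasoning on nephrogenic systemic fibrosis has its stated basis.

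Neither section gives a creatinine or eGFR limit. The sponsor may wish to set one, because the borrowed wording alone leaves open how much impairment counts and how it is detected.

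The cost is one line. Some candidates become explicitly ineligible, but nobody whom the risk section does not already exclude. How many cannot be told from the documents.

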### **Definition of Adverse Events**

The investigators will determine the seriousness, intensity, and causality of an adverse experience associated with the use of the test procedure (*i.e.*, experiences where there is a reasonable possibility that the experience may have been caused by the test procedure) based on the following definitions:

## 1. Serious Adverse Experiences

The definition of a serious adverse event (SAE) is any of the following:

- Any death that occurs while the patient is enrolled in the study including the follow-up period or within 30 days of completing the study.
- Immediately life-threatening adverse event.
- Requires inpatient hospitalization.
- Prolongation of an existing hospitalization.
- Congenital anomaly/birth defect.
- Medically important event\*
- Disability/incapacity (persistent or significant)

\*Medically important events that may not result in death, be life-threatening or require hospitalization may be considered a serious adverse experience when, based upon appropriate medical judgment, the experience may jeopardize the patient or subject and may require medical or surgical intervention to prevent one of the outcomes listed in the definition.

## 2. Unexpected Adverse Experience

An **unexpected adverse experience** is any adverse device experience, the specificity or severity of which is not consistent with those noted in the current research protocol. This refers to any adverse device experience that has not been previously observed, rather than from the perspective of such an experience not being anticipated from the pharmacologic properties of the product.

## 3. Non-serious Adverse Experiences

All other adverse experiences, not fulfilling the previous definitions, are classified as non-serious.

### **Documenting Adverse Experiences:**

All adverse experiences are to be accurately recorded on the Adverse Events & Description of AE columns of the patient's CRF. Each experience will be categorized as either: serious AE, non-serious AE, or unexpected AE (see CRF). The date of onset as well as the duration of the experience will be recorded. In addition, the method used to treat the adverse experience and the outcome of the adverse experience will also be

noted. The investigator will attempt to assess the relationship of the experience (unrelated, remote, possible, probable, related) to the test procedure.

### **Reporting SAEs, Unexpected Adverse Experiences, and Patient Deaths**

#### **1. Time-frame for Reporting:**

Any harm experienced by a participant related to the research procedure, intervention, and/or device when ALL of the following three (3) conditions are met will be reported within 7 calendar days:

1. The harm is “unexpected” when its specificity and severity are not accurately reflected in the WCMC consent document and protocol **AND**
2. The harm is “related or possibly related”, where there is a reasonable possibility that the harm may have been caused by the research procedure or intervention **AND**
3. The harm suggests that the research places subjects at greater risk of harm (including physical, psychological, economic or social harm) than was previously known or recognized

In addition to the above, any unanticipated adverse effect (any serious adverse effect on health or safety or any life threatening problem or death) will be reported within 7 calendar days that is EITHER:

1. Caused by, or associated with, a device if that effect, problem, or death was not previously identified in nature, severity, or degree of incidence in the investigational plan or IDE application (including a supplementary plan or application); **OR**
2. Any other unanticipated serious problem associated with a device that relates to the rights, safety, or welfare of participants.

2. Information to be provided by the Investigator

At the time of the report, the investigator must transmit information regarding the following:

- Underlying diagnosis and extent of disease
- Dates of procedure
- Description of event, including date of onset and duration
- Date of death (if applicable)
- Intervention(s) required
- Concomitant therapy (including regimen(s) and indication)
- Pertinent laboratory data/diagnostic test (including dates)
- Pertinent medical history
- Severity of the adverse experience
- Relationship of the adverse experience to research study treatment
- Outcome of the adverse experience

**Follow-up Information on an SAE:**

Appropriate diagnostic tests should be performed and therapeutic measures, if indicated, should be instituted. Appropriate consultation and follow-up evaluations should be carried out until the event has resolved or is otherwise explained. Follow-up data concerning the SAE (e.g., diagnostic test reports, physician's summaries, etc.) will also be submitted.

**Review of an SAE:**

After an SAE, enrollment will be halted until the DSMB reviews the SAE and determines that the study can be continued. Additionally, the PI will notify the FDA and will review each serious and unexpected adverse experience report and further evaluate the relationship of this adverse experience to the test device and to the patient's underlying disease. Based on this assessment, a decision will be made concerning the need for further action. The primary consideration governing further action is whether new findings affect the safety of other patients participating in the clinical research study. If the discovery of a new adverse experience related to the test device raises concern over the safety of its continued administration to patients, the PI will take immediate steps to

notify the IRB and all investigators participating in clinical studies of the test drugs used in this research protocol.

Further action required may include any of the following:

- Modification of the research protocol.
- Discontinuation or suspension of the research study.
- Alteration of the informed consent process by modification of the existing consent form and informing current research study participants of new findings.
- Modification of previously identified expected adverse experiences lists to include adverse experiences newly identified as test procedure-related.

